5.1 Inclusion criteria

5.1.1 Breastfeeding group

Subjects in the breastfeeding group included in this study must meet all of the following criteria:

- The $0 \sim 28$ days after birth;
- Single-child birth;
- The gestational age was from 37 to 42 weeks;
- Birth weight is 2500 ~ 4000 g;

• Parents or guardians agree to exclude the infant from participating in other interventional clinical studies during this study;

• Parents or guardians agreed to feed the infants according to the trial protocol.

5.1.2 Artificial feeding group

Subjects in the artificial feeding group included in this study must meet all of the following criteria:

- The $0 \sim 28$ days after birth;
- Single-child birth;
- The gestational age was from 37 to 42 weeks;
- Birth weight is 2500 ~ 4000 g;

• Parents or guardians agree to exclude the infant from participating in other interventional clinical studies during this study;

- Parents or guardians agreed to feed the baby according to the trial protocol;
- No exclusive breastfeeding mothers for subjective and objective reasons.

5.2 Exclusion criteria

Subjects will not be included in this trial if they meet any of the following criteria:

- Artificial assisted reproduction;
- The mother suffers from diseases that may endanger the intrauterine growth;

• The mother had gestational diabetes or severe metabolic disease, chronic disease at the time of pregnancy

• Having congenital malformations and genetic, chronic, and congenital diseases that may interfere with the investigation;

• IgE mediated milk protein allergy or factors that increase the risk of milk protein allergy;

- Having an acute infection or gastroenteritis;
- Functional gastrointestinal diseases, such as gastroparesis;
- Is participating in other clinical trials;

• The investigator was unable to determine the parents' willingness or ability to comply with the protocol requirements.

5.3 Exit standard

• Ineligible (ignored during screening, occurred during the study or found by review);

- Serious protocol deviation occurs;
- Serious non to protocol or test requirements;

[figure not shown]
• Need to terminate the designated formula due to adverse events or cause failure to continue following the trial procedures;

• Need to discontinue the designated formula or cause the inability to follow the trial procedures due to disease progression;

- Withdraw informed consent or remove informed consent;
- Misvisit.

6 research design

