Visit 1 will be performed on the 28th day after birth and the intervention period will last 332 days (slightly changed by clinic visit time) consisting of 3 visits: Visit 2 (90 ± 3 days after birth), Visit 3 (180 ± 5 days after birth), and Visit 4 (360 ± 7 days after birth). Subjects in each group will be enrolled 1:1 and based on an expected completion rate of 80%, 64 subjects are expected to complete the trial. Participants who withdrew from the study before Visit 4, failed in three contacts, met the withdrawal criteria, seriously violated the trial protocol, or met other withdrawal criteria were excluded by the investigators.

In addition, indicators and incidence of adverse events (e. g. eczema) will be recorded and compared during the study. For the purposes of this trial, adverse events were defined as any adverse and unexpected signs (including other abnormal laboratory results beyond the study plan), symptoms, disease related to participation in the clinical trial, and the disease related to the trial product.

5 subject investigated

Infants born 0 to 28 days after birth are screened and who meet all inclusion criteria and do not meet any exclusion criteria will be assigned to the breastfeeding group or randomized to the trial / control group.

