6.6 Interview

6.6.1 Visit 1

Visit 1 will be performed on the 28th day of life and the investigator will obtain the following information:

· Mode of delivery;

· Pregnancy-related complications;

· Parents' physical condition (height, weight, medical history);

· Parents' living habits (smoking history, drinking history, exercise habits);

· Parents' social and economic background (education level, employment status);

· Growth and development parameters (height, head circumference, chest circumference, body weight);

- Stool samples (16S rRNA, SCFAs, sIgA);
- · Gastrointestinal comfort survey and questionnaire;
- · Questionnaire on baby crying condition;
- · Questionnaire on infant diarrhea;
- · Questionnaire on upper respiratory tract infection in infants;

⁵⁷Steenhout P, Sperisen P, Martin F, et al.Term Infant Formula Supplemented with Human Milk Oligosaccharides (2' Fucosyllactose and Lacto - N - neotetraose) Shifts Stool Microbiota and Metabolic Signatures Closer to that of Breastfed Infants[J].The FASEB Journal, 2016, 30.

- · The Bristol Stool Classification Questionnaire;
- · Past medical history and current medical history.

6.6.2 Visit 2

Visit 2 will be conducted on Birth Day 90 with a window of 3 days and the investigator will measure and obtain the following information:

· Growth and development parameters (height, head circumference, chest circumference, body weight);

- · Gastrointestinal comfort survey and questionnaire;
- · Questionnaire on baby crying condition;
- · Questionnaire on infant diarrhea;
- · Questionnaire on upper respiratory tract infection in infants;
- · The Bristol Stool Classification Questionnaire;
- · Adverse events and serious adverse events.

6.6.3 Visit 3

Visit 3 will be conducted on Post Birth Day 180 with a window of 5 days and the investigator will measure and obtain the following information:

· Growth and development parameters (height, head circumference, chest circumference, body weight);

- Blood samples (hsCRP, analysis of lymphocyte subsets, amino acids, osteocalcin, alkaline phosphatase, albumin);
- Stool samples (16S rRNA, SCFAs, sIgA);
- · Gastrointestinal comfort survey and questionnaire;
- · Questionnaire on baby crying condition;
- · Questionnaire on infant diarrhea;
- · Questionnaire on upper respiratory tract infection in infants;
- · The Bristol Stool Classification Questionnaire;
- · Adverse events and serious adverse events.

6.6.4 Visit 4

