6.7 Subjects stopped / withdrew from the trial

The guardian of the subject has the right to withdraw the infant from the trial at any time. In addition, the investigator may discontinue the subject at any time if the investigator considers it necessary for reasons including:

• Ineligible (ignored during screening, occurred during the study or found by review);

- Serious protocol deviation occurs;
- Serious non to protocol or test requirements;
- Termination of the designated formula or failure to follow the trial procedures due to an adverse event;

• Need to discontinue the designated formula or cause the inability to follow the trial procedures due to disease progression;

- Withdraw informed consent or remove informed consent;
- Misvisit.

If a subject withdraws from the trial due to an adverse event, the investigator will schedule a follow-up visit or telephone visit until the adverse event is resolved or is stable. Data collected before withdrawal will be used for analysis. If a subject withdraws from the trial, the subject will not be replaced. The reason for the withdrawal will be documented in the case report form.

7 Research products

7.1 burden

(1) Ingredients list of test milk powder

The test milk powder was produced by Feihe (Jilin) Dairy Co., LTD. Three formulations were used for infants aged 0-3 months, 3-6 months and 6-12 months respectively. All products are produced in strict accordance with Good Production Practice (GMP), and all indicators meet the requirements of relevant standards and regulations. Compared with the control milk powder, 2 ' -fucinose based lactose, lactose-N-new tetrosaccharide, bifidobacterium longum BB536 are the added ingredients unique to the test milk powder, and the ingredients are as follows:

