8.2 Secondary end point

Inflammation index: serum hsCRP; nutritional index: serum albumin; growth and development index: height, weight, head circumference, chest circumference; immune index: fecal sIgA, blood lymphocyte subgroup; bone development index: osteocalcin, alkaline phosphatase; tolerance index: survey of infant gastrointestinal comfort, infant sleep crying, infant diarrhea and upper respiratory tract infection, infant stool Bristol stool classification; cognitive development index: Bailey Infant Development Scale (IV edition), serum amino acids.

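### The exit, exclusion, adverse-event and endpoint passages conflict, so on one literal reading an on-study infection or gastroenteritis is both a secondary endpoint and a reason to leave the trial

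*Protocol*

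**What the plan says.** **Exit.** Protocol 5.3 lists, with no qualifier, "Ineligible (ignored during screening, occurred during the study or found by review"). Section 6.7 repeats the item under a discretionary lead-in: "the investigator may discontinue the subject at any time if the investigator considers it necessary for reasons including" the listed reasons. Section 4 is firmer and says that participants who "met the withdrawal criteria, seriously violated the trial protocol, or met other withdrawal criteria were excluded by the investigators".

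**Exclusion.** The list in 5.2 contains "Having an acute infection or gastroenteritis", "Functional gastrointestinal diseases, such as gastroparesis", and IgE-mediated milk protein allergy or factors raising its risk. None of these items carries a time limit, although the sentence that opens the list is worded as an entry test.

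**Endpoints.** Section 8.2 has as a secondary endpoint the "tolerance index: survey of infant gastrointestinal comfort, infant sleep crying, infant diarrhea and upper respiratory tract infection, infant stool Bristol stool classification". The diarrhea and respiratory infection questionnaires are listed in 6.6 at all four visits (days 28, 90, 180 and 360).

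**On-study illness and data handling.** Section 10.2 says that an adverse event may lead to withdrawal or may not. Under 6.7, data collected before withdrawal are analysed and withdrawn infants are not replaced. Section 9.2 rules out imputation. In 9.3 the FAS, the main efficacy set, needs only Visit 1; the PPS needs all visits.

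**The concern.** An infant enrolled healthy who later has gastroenteritis or an acute respiratory infection now shows a condition on the exclusion list. If that counts as ineligibility arising on study, the event that 8.2 sets out to measure is also a reason to stop measuring. The protocol does not say whether it counts, and its passages on what follows differ in force.

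Three things are at stake. First, loss to follow-up would depend on an outcome, and would differ between test and control if the formulas differ in infection or gut illness. Secondly, stool for the primary endpoint is taken only at days 28, 180 and 360, so an infant exited before day 180 has no stool after Visit 1. Thirdly, discretion without guidance in a multicenter trial lets the same illness end follow-up at one site and not at another.

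**Working it through.** **1. The plan's own figure.** 80 enrolled per group with 20% loss gives 80 × (1 − 0.20) = 64 completers, as stated in Section 4 and 6.5.2. The plan does not break the 20% down by cause.

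**2. What can arise during the study?** The exit item has three parts. Two of them (missed at screening, found at review) already cover errors made at entry, so the third adds ineligibility that arises later. Gestational age, birth weight, singleton birth, assisted reproduction and maternal disease in pregnancy are fixed before enrolment. What can newly arise is joining another trial, a change in the parents' willingness or ability to comply, or an illness: acute infection, gastroenteritis, functional gastrointestinal disease or allergy. The literal reading that includes illness is therefore available.

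**3. How far does it overlap with the endpoints?**

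| Endpoint in 8.2 | Matching item in 5.2 |
|---|---|
| Diarrhea | Gastroenteritis: direct |
| Upper respiratory infection | Acute infection: direct |
| Gastrointestinal comfort | Functional gastrointestinal disease: indirect |
| Sleep and crying, Bristol stool type | None |

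**4. What is lost on exit?** Kept: everything up to exit, including the event itself, and membership of the FAS. Lost: scheduled data after exit, namely stool and blood at days 180 and 360, growth at the remaining visits, the day-360 Bayley assessment, and membership of the PPS. Without imputation, FAS membership supplies no day-180 or day-360 value.

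**5. Upper bound on the loss.** The documents give no illness rate. Assume a constant Poisson rate r per infant-year, and that every qualifying illness leads to exit. From day 28 to day 360 is 332 days; from day 28 to day 180 is 152 days.

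- Share meeting the rule by day 360: 1 − exp(−r × 332/365.25)
- Share meeting it by day 180: 1 − exp(−r × 152/365.25)
- Remaining of 80: 80 × (1 − share by day 360). With a further, independent 20% loss: 64 × (1 − share by day 360)

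| r (assumed) | By day 180 | By day 360 | Remaining of 80 | With a further 20% loss |
|---|---|---|---|---|
| 0.25 | 10% | 20% | 64 | 51 |
| 0.5 | 19% | 37% | 51 | 41 |
| 1 | 34% | 60% | 32 | 26 |
| 2 | 56% | 84% | 13 | 10 |

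Partial application scales the rate. If one illness in four leads to exit at r = 1, the effective rate is 1 × 0.25 = 0.25 and the first row applies. That row alone uses up the planned 20%.

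**6. Difference between arms.** If 30% of test and 50% of control infants were exited (assumed), on top of 20% other loss, completers would be 64 × 0.7 ≈ 45 and 64 × 0.5 = 32.

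**7. Effect on infection counts.** At assumed rates of 2 and 1.6 a year over 332 days, expected episodes per infant are 1.82 and 1.45, a difference of 0.36 before rounding. If only the first episode is seen, the means are 0.838 and 0.766, a difference of 0.07. This shrinkage applies to counts or proportions per infant. Under the same constant-rate model, events divided by infant-time up to the first event still recover 2 and 1.6.

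**The case against.** The strongest case is that the eligibility lists are entry tests and cannot be standing conditions. Being 0 to 28 days old is an inclusion criterion, so continuous re-application would make every infant ineligible on day 29. Section 10.2 contemplates adverse events that do not lead to withdrawal. Section 5.3 has separate items for adverse events and disease progression, limited to cases where the formula must stop or procedures cannot be followed; these would be largely redundant for infections if any acute infection already meant exit. Section 6.7 is discretionary, and infection questionnaires at Visits 2 to 4 presuppose continued follow-up. The trial is also described as exploratory (Section 4), with inference for reference only (9.2).

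Most of this stands, and it defeats a stronger reading that a reader might infer: that exit is automatic at the first infection. The documents do not support that. Nor do they support saying that all tolerance endpoints trigger exit, since crying and stool type match no exclusion criterion, or that the flora comparison is biased in a known direction.

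What the objection does not remove is the ambiguity. The day-29 argument shows that some criteria must be entry-only, but the protocol does not say which, while 5.3 expressly carries ineligibility past entry. Section 4 is worded as exclusion, against the discretion in 6.7 and 10.2. Keeping earlier data and FAS membership limits the damage but does not restore the later samples.

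**Conclusion.** The point holds as a conflict between passages, not as an automatic rule. Sections 5.3, 6.7, 4 and 10.2 do not agree on what follows when an infant develops a condition listed in 5.2, and two of those conditions overlap directly with endpoints in 8.2. Wherever a site applies the literal reading, loss depends on outcome and possibly on arm, and it reaches the day-180 and day-360 stool samples behind the primary endpoint.

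The size cannot be determined from the documents. The range of 20% to 84% rests on assumed rates of 0.25 to 2 per infant-year, a constant Poisson rate, and every illness leading to exit; it is a ceiling at each rate, not a forecast. Severity: should-fix. Confidence: moderate.

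**What to change.** Reconcile 5.3, 6.7, Section 4 and 10.2 with 5.2 and 8.2 by a wording amendment that:

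- states which eligibility criteria are judged at screening only and which can arise later as ineligibility;
- gives one account of whether meeting an exit criterion excludes an infant or leaves a decision to the investigator, used in all four sections;
- separates the decision to stop the assigned formula, left to the existing clinical wording, from the end of data collection, so that an endpoint event alone does not end scheduled visits and samples while consent continues.

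No clinical rule on formula or illness is proposed here.

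The cost is the amendment, its notification to the ethics committee and a briefing of sites; no visits or assays are added. The downside is that some stools will come from recently ill infants. These can be flagged from the illness questionnaires already collected.

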6.1 Test flow chart

6.2 recruit

The investigator will identify suitable infants, contact their parents or guardians by telephone and otherwise, and make an appointment for informed consent and subject screening.

6.3 informed consent

The subject's guardian must personally sign the informed consent form and date before conducting any trial process. If the version is updated, contact the guardian to sign the latest version of the informed consent.

A written version of the informed consent was provided to the guardian of the subject, and the investigator should explain the following: the nature of the trial; the content of the subject; the requirements of the protocol; known side effects and any risks involved in participation. The guardian should also be clearly informed that the baby can be withdrawn from the study at any time for any reason, without affecting the baby's medical treatment, legal rights, and no obligation to provide a reason for the withdrawal.

The guardian of the subject was allowed enough time to consider the relevant information and the opportunity to ask the researcher, their GP or other independent party to decide whether to enroll the infant in the trial. The subject's guardian will then sign and date the informed consent form, followed by the investigator giving the informed consent. The investigator who gave the informed consent must have the appropriate qualifications and experience and must be authorized by the principal investigator at each institution. A copy of the signed informed consent form will be given to the subject's guardian for retention and the original remains at the study institution.

6.4 dressing by screening

The investigator will ask the guardian, investigate the basic information of the subject infant, fill in the screening record and the Subject Screening and Enrollment Registration Form, and the infant will be included in the study after meeting the inclusion and exclusion criteria. If the guardian chooses to exclusively breastfeed the infant, the infant will be assigned to the breastfeeding group; if due chooses artificial or mixed feeding, the infant will be randomized to the trial or control group.

6.5 randomization

6.5.1 Random group table

Randtrial block randomization. The randomization tables were generated simulated on a computer by an unblinded statistician using the SAS software according to the random number table. Trial or control milk powder were coded according to the randomization table. Each center will compete for entry. In clinical operation, the authorized investigator or the research assistant will distribute the test or control milk powder according to Powder No. Any deviations should be truthfully recorded for evaluation before data analysis.

6.5.2 Sample size and calculation basis

 J57 The study enrolled 88 test group, 87 control infants, 34 breastfed infants with 1g / L 2 ' / FL and 0.5 g / L LNnT to formula-fed infants, control formula-fed infants and breast-fed infants. All the fecal samples available at 3 months of age were 58 in the test group, 65 in the control group, and 34 in the breastfeeding group. They evaluated the microbiota using 16S rRNA gene sequencing and metagenomics, and found that the microbiota composition of the test group was different from that of the control group and closer to that of the breastfeeding group. In this study, the experimental group, control group and breastfeeding group are planned to include 80 subjects, calculated by the shedding rate (failure rate) of 20%. The effective sample size of each group is expected to be 64 cases, which can meet the study needs.

6.6 Interview

6.6.1 Visit 1

Visit 1 will be performed on the 28th day of life and the investigator will obtain the following information:

· Mode of delivery;

· Pregnancy-related complications;

· Parents' physical condition (height, weight, medical history);

· Parents' living habits (smoking history, drinking history, exercise habits);

· Parents' social and economic background (education level, employment status);

· Growth and development parameters (height, head circumference, chest circumference, body weight);

- Stool samples (16S rRNA, SCFAs, sIgA);
- · Gastrointestinal comfort survey and questionnaire;
- · Questionnaire on baby crying condition;
- · Questionnaire on infant diarrhea;
- · Questionnaire on upper respiratory tract infection in infants;

⁵⁷Steenhout P, Sperisen P, Martin F, et al.Term Infant Formula Supplemented with Human Milk Oligosaccharides (2' Fucosyllactose and Lacto - N - neotetraose) Shifts Stool Microbiota and Metabolic Signatures Closer to that of Breastfed Infants[J].The FASEB Journal, 2016, 30.

- · The Bristol Stool Classification Questionnaire;
- · Past medical history and current medical history.

6.6.2 Visit 2

Visit 2 will be conducted on Birth Day 90 with a window of 3 days and the investigator will measure and obtain the following information:

· Growth and development parameters (height, head circumference, chest circumference, body weight);

- · Gastrointestinal comfort survey and questionnaire;
- · Questionnaire on baby crying condition;
- · Questionnaire on infant diarrhea;
- · Questionnaire on upper respiratory tract infection in infants;
- · The Bristol Stool Classification Questionnaire;
- · Adverse events and serious adverse events.

6.6.3 Visit 3

Visit 3 will be conducted on Post Birth Day 180 with a window of 5 days and the investigator will measure and obtain the following information:

· Growth and development parameters (height, head circumference, chest circumference, body weight);

- Blood samples (hsCRP, analysis of lymphocyte subsets, amino acids, osteocalcin, alkaline phosphatase, albumin);
- Stool samples (16S rRNA, SCFAs, sIgA);
- · Gastrointestinal comfort survey and questionnaire;
- · Questionnaire on baby crying condition;
- · Questionnaire on infant diarrhea;
- · Questionnaire on upper respiratory tract infection in infants;
- · The Bristol Stool Classification Questionnaire;
- · Adverse events and serious adverse events.

6.6.4 Visit 4

Visit 4 will be performed on Post Birth Day 360 with a window of 7 days and the investigator will measure and obtain the following information:

· Growth and development parameters (height, head circumference, chest circumference, body weight);

- · Bailey Infant Development Scale (Version IV);
- Blood samples (hsCRP, lymphocyte subsets, amino acids, osteocalcin, alkaline phosphatase, albumin);
- Stool samples (16S rRNA, SCFAs, sIgA);
- · Gastrointestinal comfort survey and questionnaire;
- · Questionnaire on baby crying condition;
- · Questionnaire on infant diarrhea;
- · Questionnaire on upper respiratory tract infection in infants;
- · The Bristol Stool Classification Questionnaire;
- · Adverse events and serious adverse events.

